#### **5.2.2.1 Cell-free DNA (cfDNA)/Circulating Tumor DNA (ctDNA), Mutational Panels, and Plasma Banking**

- Collect blood in cell-free DNA (e.g., Streck BCT/collection tubes); gently invert the tubes 8-10 times immediately after collection.
- Plasma will be isolated and frozen at -80°C until analysis (e.g., centrifuged at 1800 x g for 10 minutes at room temperature; plasma transferred/frozen in aliquots of 1.5-2mL each).

#### **5.2.2.2 Immune Subsets/Markers and Peripheral Blood Mononuclear Cells (PBMCs)**

- Collect blood in Cell Preparation Tubes with sodium citrate (e.g., blue/black speckled top); gently invert tubes 8-10 times immediately after collection.
- PBMCs will be isolated per routine laboratory techniques

#### **5.2.2.3 Cytokines and Serum Banking**

- Collect blood in Serum Separator Tubes (e.g., red/gray or red/yellow top); gently invert the tubes 8-10 times immediately after collection and allow the blood to clot at room temperature for approximately 30 minutes.
- Serum will be isolated and frozen at -80°C until analysis (e.g., centrifuged at 1200 x g for 5 minutes at 4°C; serum transferred/frozen in aliquots of 1.5-2 mL each).

#### **5.2.2.4 Magrolimab Pharmacokinetics (PK) and Anti-Drug Antibody (ADA) Samples**

See [Appendix F](#) for additional details.

- Fill Red Top Serum Separator Tubes COMPLETELY, as far as the vacuum will allow.
- Mix immediately by gently inverting the tube 5 times.
- Allow blood to clot undisturbed for 30 minutes (max. 60 minutes), tube standing upright.

- Centrifuge tube within 1 hour of collection for 10-15 minutes at 1800 g until clot and serum are separated by a well –formed polymer barrier. If serum and cells have not completely separated, re-centrifuge the specimen for an additional 6-8 minutes.
- Transfer serum, using a transfer pipette, into the Transport Tube (s).
- Allow enough space between serum and tube caps to account for expansion during freezing. Do not overfill.
- Record the subject ID number on the specimen label.
- Wrap a small piece of parafilm around the cap of the transport tube. See parafilm instructions below.
- Store serum samples for a minimum of 8 hours at -80°C until shipment to PPD Richmond.

### **5.2.3 Blood Samples – NCI Laboratory of Pathology**

The blood samples for flow cytometry should be sent to the NCI Laboratory of Pathology; please contact NCI Laboratory of Pathology (LP) for questions and for notification of samples.

#### **5.2.3.1 Flow cytometry**

- Collect blood, bone marrow, and/or lymph node samples in appropriate tubes (e.g., NaHep/sodium heparin, EDTA, etc.) tubes; gently invert the tubes 8-10 times immediately after collection.
- Send samples to the NCI LP for specialized flow cytometry processing and analysis.
- Studies to be performed on these samples include multi-parameter flow cytometry to determine the percentage of aberrant lymphoma cells. Reagents to be used include but are not limited to characteristic B-cell markers including: CD10, CD19, CD20, CD21, CD22, CD23, Bcl-2, Bcl-6, CD79B, kappa and lambda light chain as well as various T-cell markers including: CD3, CD5, CD4 and CD8.

### **5.2.4 Tissue Samples**

#### **5.2.4.1 Archival tissue**

Archival block(s) or slides (i.e., at least 15 unstained slides, 5-microns) is required at baseline; these may also be required in follow-up in case of future routine procedures or in case additional tissue is needed even in the event of optional tumor biopsy.

#### **5.2.4.2 Lymph node excision or core needle biopsy**

Lymph node excision or core needle biopsy will be performed per routine standard of care, by Surgery Consultants or Interventional Radiology, as appropriate. A procedure-specific consent form will be signed by the patient prior to the procedure. Every attempt will be made to perform excisional lymph node biopsies to obtain the best quality tissue for translational investigation. Consideration of alternative biopsy methods (e.g., core needle biopsy) will only be made if follow-up excisional biopsy is not possible/safe or patient is unwilling to undergo repeat excisional lymph node biopsy.

In the event that a surgical biopsy procedure is performed, more than one lymph node and at more than one anatomic site may be collected, provided the additional procedures are not unacceptable risk to the patient. In the event of core needle biopsy, these are obtained typically by using a 16-18G needle at the discretion of the provider performing the procedure. Conscious sedation may be used, if warranted, and the use and risks are acceptable to the patient. General anesthesia will

not be performed to obtain biopsies for research purposes. The type of procedure to be done and manner in which it will proceed (e.g., excision/core, single vs. multiple sites of biopsy) will be discussed with the patient prior to the biopsy procedure; if CT guidance will be used for a research biopsy procedure, research radiation exposure will be discussed with the patient. Similar procedure may be followed for extranodal disease/masses. The patient will be reminded that all sampling for research is voluntary.

#### 5.2.4.3 Sample handling/processing

When performed, excisions or core biopsies will be placed in sterile collection/core cylinder tubes (e.g., formalin); gently invert/inspect tubes with media 8-10 times immediately after collection to ensure the core(s) is completely immersed in the media.

Tissue samples will be handled/processed as below prior to planned analyses, as appropriate:

- Any required routine review for histopathologic confirmation of diagnosis and/or grade will occur per standard of care (e.g., H&E, immunohistochemistry), if required.
- Formalin samples will be fixed and paraffin-embedded per routine techniques.

### 5.2.5 Other Samples

#### 5.2.5.1 Germline DNA

Germline DNA will be collected by blood, buccal swab, and/or saliva samples (preferred). These will ideally be collected at baseline; however, may be collected at any point on study based on supplies. Standardized, commercial collection kits or tubes will be used (e.g., 1, 5-10 mL K2EDTA tube for blood; Isohelix SK-1 for buccal swabs; Salvette/Oragene® for saliva). In the case of buccal swabs, two (2) samples may be collected in order to ensure adequate DNA collection.

The samples will be processed and DNA extracted/isolated per kit instructions and established techniques. These will be handled by [name] lab (see Section [5.2.2](#) for contact information).

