### **1.2.3 Indolent B-cell Leukemias: Chronic Lymphocytic Leukemia and Mantle Cell Lymphoma**

Chronic lymphocytic leukemia (CLL)/small lymphocytic lymphoma (SLL) (henceforth called CLL) and mantle cell lymphoma (MCL) are also incurable B-cell malignancies that are considered separately in this protocol because they are frequently associated with a leukemic component that manifests with high levels of circulating tumor cells. These patients may be more susceptible to specific toxicities such as tumor lysis syndrome (TLS), and hence, will receive a lower target dose of venetoclax on this protocol.

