**Research Samples Calendar – Tissue/Other:**

| Sample  | Collection Details*  | Time Points  | Supervising Laboratory/
Investigator |
|---|--|--|---|
| Tissue Samples                                   |  |  |   |
| Archival and/or Fresh Tissue Biopsy                     | 
 
FFPE (block or slides); biopsy is required if archival is not adequate or unavailable
 
Excision (single or multiple nodes) or core (6 passes); placed in formalin/FFPE and media, as appropriate
 
 | 
 
Baseline; if required for adequate tissue
 
During 1st cycle (Cycle -2; preferably day 8) of doublet therapy with magrolimab + obinutuzumab in window period (optional)†
 
At disease progression/end of treatment
 
   | [name], [name],
NCI LP              |
| Tissue/Imaging Analyses                                 | No additional tissues or imaging will be performed for these analyses, only use of already collected samples and/or imaging, as described in Section 5.3.6   |  | [name]                                  |
| Other Samples                                    |  |  |   |
| Germline DNA  | 
 
Blood, Buccal swab, or Saliva (preferred)
 
  | 
 
Baseline
 
   | [name]                                    |
| Bone marrow aspirate ( $\pm$ flow cytometry) and biopsy | 
 
Aspirate (<math>\pm</math> flow cytometry) (SOC; heparinized tubes or EDTA/sodium heparin or formalin, as appropriate)
 
Biopsy (SOC; formalin or no media, as appropriate)
 
                       | 
 
Baseline
 
During 1st cycle of doublet therapy with magrolimab + obinutuzumab (Cycle -2; preferably day 8) in window period (optional)†
 
At disease progression or suspicion of CR
 
After Cycle 6 of triplet therapy (magrolimab + obinutuzumab + venetoclax) in patients with involvement at baseline. For patients with no baseline bone marrow involvement, biopsy may be performed per investigator's discretion.
 
 | [name],
NCI LP\                        |

\*Tubes/media may be adjusted at the time of collection based upon materials available or to ensure the best samples are collected for planned analyses.

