#### **5.3.5 DNA/RNA Sequencing**

Genomic DNA and total RNA will be extracted from tumor samples using a Qiagen All-prep kit. For individual target genes that are recurrently mutated in indolent NHL, classical Sanger sequencing will be performed on PCR amplicons, using primers surrounding the known sites of mutation. To broadly assess mutations, next generation sequencing (e.g., on an Illumina HiSeq 2000 platform) will be employed, using a paired end sequencing strategy of libraries constructed from tumor DNA. DNA will either be sequenced in its entirety from a whole genome library or will be first enriched for exonic sequences using the Agilent Sure Select system, aiming for 30X or 100X average coverage per base, respectively. The sequence fragments will be mapped back to the genome using the BWA algorithm. Of sequences overlapping a particular base pair in the genome, the percent mutant calls greater than 20% with a minimum of 25X coverage will be

considered as an arbitrary threshold for single nucleotide variants (SNVs). SNVs that are not present in the matched normal sample will be considered candidate somatic mutations.

A related technology, RNA-Seq, utilizes RNA from the tumor specimen to create a cDNA library for high-throughput sequencing. RNA-seq will be performed using Illumina kits followed by high-throughput sequencing on an Illumina HighSeq 2000 machine. The cutoffs for coverage and percent mutant calls mentioned above will also be used to identify putative SNVs. RNA sequencing will also be used to read out digital gene expression across the genome as described.

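### Unsorted blood is an allowed germline normal in every histology, so in patients with circulating tumor the matched-normal filter can remove true clonal mutations from exploratory tumor-DNA calls

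*Combined protocol and SAP*

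**What the plan says.** Section 5.2.5.1 names three germline sources: "Germline DNA will be collected by blood, buccal swab, and/or saliva samples (preferred". The Research Samples Calendar for tissue and other samples in Section 5.1 repeats them as "Blood, Buccal swab, or Saliva (preferred". In both places saliva is preferred but not required, and neither limits the choice by histology. The blood option is a plain EDTA tube ("tube for blood; Isohelix SK-1 for buccal swabs"); no sorting or B-cell depletion is mentioned. On timing: "These will ideally be collected at baseline; however, may be collected at any point on study based on supplies".

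Section 5.3.5 sets the somatic rule: "SNVs that are not present in the matched normal sample will be considered candidate somatic mutations". Its only numeric criterion for an SNV is "the percent mutant calls greater than 20% with a minimum of 25X coverage", which it calls arbitrary. It does not say whether that criterion also decides presence in the normal. Planned depth for the tumor libraries is given as "aiming for 30X or 100X average coverage per base, respectively", for whole genome and exome in that order. No depth is given for the normal.

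Section 1.2.3 describes CLL and MCL as "frequently associated with a leukemic component that manifests with high levels of circulating tumor cells". Section 2.2.6 requires peripheral-blood flow cytometry at screening, so circulating disease will be known for each patient before treatment.

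**The concern.** A matched normal serves to identify inherited variants, so it must be largely free of tumor. Blood from a patient with a leukemic component is a mixture of normal and tumor cells. Under the Section 5.3.5 rule, a tumor mutation visible in that mixture is treated as inherited and dropped. Nothing in Sections 5.1, 5.2.5.1 or 5.3.5 bars blood in such patients, checks the normal for tumor, or adjusts the calls.

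At stake are the exploratory objectives on mutational signatures of response and resistance (Sections 1.1.3 and 10.4.9). A dropped mutation looks the same as a wild-type result. The chance of loss rises with circulating burden, so where blood is used the error would depend on disease burden and would not be random noise. Expansion cohorts of 6 to 18 patients give little room to absorb a few wrongly emptied profiles.

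**Working it through.** The plan gives no error rate or sample size for this step, so there is no figure to reproduce. The calculation below shows when the rule causes loss.

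**Inputs from the documents.** Cutoff >20% mutant reads with at least 25X coverage; depths 30X and 100X (Section 5.3.5).

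**Assumptions.**
- f is the tumor share of nucleated blood cells at the draw. The documents do not give it, so a range is shown.
- The mutation is clonal and heterozygous in a diploid region.
- The normal is sequenced at the same depth D as the tumor.

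**Formula.** Expected mutant read fraction in the blood normal: v = f/2. Mutant reads X follow a Binomial(D, v) distribution. The variant is discarded when X reaches the count taken to mean present. Two readings:

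- (a) The plan's own cutoff applies to the normal: X/D > 0.20, so X ≥ 7 at 30X and X ≥ 21 at 100X. The expected fraction passes the cutoff when f/2 > 0.20, that is, f > 0.40.
- (b) Two mutant reads suffice: P = 1 − (1−v)^D − D·v·(1−v)^(D−1). This rule is not in the plan and serves as a stricter comparison.

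**Probability that a true clonal mutation is removed**

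| f | v | (a) 30X | (a) 100X | (b) 30X | (b) 100X |
|---|---|---|---|---|---|
| 0.05 | 0.025 | 0.00 | 0.00 | 0.17 | 0.72 |
| 0.1 | 0.05 | 0.001 | 0.00 | 0.45 | 0.96 |
| 0.2 | 0.10 | 0.03 | 0.001 | 0.82 | 1.00 |
| 0.4 | 0.20 | 0.39 | 0.44 | 0.99 | 1.00 |
| 0.6 | 0.30 | 0.84 | 0.98 | 1.00 | 1.00 |
| 0.8 | 0.40 | 0.98 | 1.00 | 1.00 | 1.00 |

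Worked case for (b), f = 0.2 at 30X: v = 0.10; 0.9^30 = 0.042; 30 × 0.10 × 0.9^29 = 0.141; 1 − 0.042 − 0.141 ≈ 0.82.

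**Scale for f.** Table 19 and Section 4.1.2.4 use an absolute lymphocyte count of 25 × 10^9/L as a tumor-lysis risk threshold. If all of those lymphocytes were tumor, with an assumed 3 to 8 × 10^9/L of other leukocytes, f would lie between 25/(25+8) = 0.76 and 25/(25+3) = 0.89. Under reading (a), removal would then exceed 0.98 at 100X. At 30X it would lie between the values for f = 0.6 and f = 0.9, that is, 0.84 and 0.996. The threshold is a risk category and says nothing about how many patients will reach it.

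**With a tumor-free normal** (f = 0), v = 0 and the filter removes no true somatic variant apart from sequencing error.

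**The case against.** The case for leaving the text alone has real substance.

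- **Blood is a fallback.** Saliva is preferred, and Appendix G points the same way: its germline row and footnote 14 name saliva and buccal swabs. This stands, and makes the loss conditional. But Sections 5.1 and 5.2.5.1 still list blood without restriction, and a preference does not exclude it.
- **At low burden the plan's own cutoff protects the calls.** Under reading (a), loss at f = 0.2 is 0.03 at 30X and 0.001 at 100X. This stands if the cutoff does apply to the normal, which the plan does not say.
- **Recurrent genes have other routes.** Section 5.3.5 plans Sanger sequencing at known mutation sites with no germline filter stated, and carries only the coverage and percent cutoffs over to RNA-Seq. Section 5.3.1 plans probes such as TP53/D17Z1 and D11Z1/ATM for CLL and IGH-CCND1 for MCL. Section 2.2.4 covers 17p deletion by karyotype. This stands in part: FISH and karyotype detect structural and copy-number changes, so for point mutations the cover comes mainly from Sanger and RNA-Seq.
- **Methods are left open.** Section 5.3 defers exact methods until samples are ready, and a germline sample drawn late, after tumor has cleared, could carry little tumor. Both are true. Neither is a safeguard, since baseline is the stated ideal and a tumor-rich normal cannot be fully repaired by later choice of software.

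A reader might go further and infer that driver mutations in CLL and MCL will be deleted as a matter of course, that all 18 expansion patients in those cohorts (12 MCL, 6 CLL) plus Cohort 2 are exposed, or that one stray read is enough to discard a variant. The documents support none of these. Blood need not be the source used, circulating disease is described as frequent but not universal, and no single-read rule appears.

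**Conclusion.** The gap is real but conditional. As written, the plan permits a normal that may be largely tumor and then subtracts whatever that normal contains. Where unsorted blood is used and f is well above 0.4, most clonal heterozygous mutations would be lost from the tumor-DNA calls even under the lenient reading (0.98 at 100X for f = 0.6). Below about f = 0.2 the loss is negligible under that reading, but substantial if two reads count as present. These figures rest on the assumed range of f, diploid clonal heterozygosity, and equal depth in tumor and normal.

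The effect is confined to exploratory mutational analyses. The safety primary endpoint, the secondary endpoints (including flow-based MRD in CLL) and the sample size are unaffected. How many patients would be affected cannot be stated from the documents. This is a cheap improvement that protects the correlative work; it does not threaten the trial's main conclusions.

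**What to change.** **Sections 5.1 and 5.2.5.1.** State that unsorted blood is not used as the matched normal for any patient, in any histology, with circulating disease on the screening peripheral-blood flow cytometry. Use the non-blood sources already listed: buccal swab, with the second swab Section 5.2.5.1 already allows if needed, or saliva checked for tumor contamination. The check is prudent because the documents do not address whether saliva might carry blood cells.

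**Section 5.3.5.** Give the read threshold and minimum depth that define presence in the matched normal. Flag any normal that may contain tumor, or use a calling method that allows for tumor in the normal.

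**Cost.** Wording changes in three places, lower DNA yield from non-blood samples, and slightly more analysis work. The sample types and the screening test that would trigger the restriction are already in the protocol.

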#### 5.2.5.2 Bone marrow aspiration ( $\pm$ flow cytometry) and core biopsy

Bone marrow collection will be performed per routine standard of care. A procedure-specific consent form will be signed by the patient prior to the procedure. Attempt will be made to collect both bone marrow aspirate and core biopsy. If required, the procedure may be performed under conscious sedation per the discretion of the investigator.

- Bone marrow aspirate and flow cytometry samples will be placed in sterile collection tubes (e.g., heparinized tubes or containing EDTA/sodium heparin or formalin, as appropriate); gently invert tubes 8-10 times immediately after collection.
- Core biopsies will be placed in sterile collection/core cylinder tubes (e.g., formalin or no media); gently invert/inspect tubes with media 8-10 times immediately after collection to ensure the core(s) is completely immersed in the media.
- Studies to be performed on these samples include cell analysis and histological (e.g., H&E), immunohistochemical (IHC)/fluorescence in situ hybridization (FISH) review/testing, and other analyses per established techniques (e.g., PD-1/PD-L1, BCL2, MUM1, Ki67, etc.).

### **5.3 BIOMARKER AND RESEARCH METHODS**

The technology platforms that are able to interrogate genomic structure and function are constantly in flux; therefore, the exact nature of the methodologies that will be employed will be assessed at the time that the samples are collected and ready for analysis.

The following are technologies that are currently in use for each planned analysis:

#### **5.3.1 Tumor Profiling**

Immunohistochemical (IHC) analyses, including FISH for BCL2 will be performed on every FL sample. For all patients with MCL, IGH-CCND1 will be performed. D6Z1/MYB, D12Z3/MDM2, D11Z1/ATM, D13S319/LAMP1 and TP53/D17Z1 will be done on every patient's baseline CLL tumor biopsy, if available. The routine IHC panel for diagnosis of indolent lymphomas will be performed on tumor tissue samples, including but not necessarily limited to CD3, CD5, CD10, CD20, CD21, CD23, BCL2, BCL6, MUM1 and MIB-1.

#### **5.3.2 Microenvironment Tissue Profiling**

Immunohistochemical (IHC) analyses will take to assess for contribution of the tumor microenvironment. IHC that will be performed may include, but are not necessarily limited to: CD3, CD4, CD8, CD20, CD45RO, CD57, CD68, FOXP3, Granzyme B, LAG3, PD-1/PD-L1 (H-score), SIRP $\alpha$ , CD14, CD33, CD47, CD163 and/or CD206.

#### **5.3.3 Immune Subset Analysis**

Peripheral blood mononuclear cells (PBMC) will be assessed using multiparameter flow cytometry for immune subsets including but not necessarily limited to CD8+ T-cells, CD4+Foxp3- T-cells, Tregs, Tex, Th1, Th2 and Th17+ CD4+ T-cells, monocyte subsets, macrophage subsets, and MDSC subsets. Assessment may include functional markers, i.e., PD-1, Tim-3, CTLA-4, PD-L1, HLA-DR, Ki67, CD47, SIRP $\alpha$  and/or CD40.

#### **5.3.4 Histo-cytometry/Multiplex Staining Technologies**

Tissues samples will be provided to the laboratory of [name] (NIAID/NIH) for recently developed multiplex staining technologies in 2D and 3D. [name] laboratory (NIAID/NIH) will return confocal images and quantitative analyses of these images in figure format for interpretation and analysis. [name] group (NIAID/NIH) will not have direct access to the key that links sample identifiers with personally-identifiable information.

#### **5.3.5 DNA/RNA Sequencing**

Genomic DNA and total RNA will be extracted from tumor samples using a Qiagen All-prep kit. For individual target genes that are recurrently mutated in indolent NHL, classical Sanger sequencing will be performed on PCR amplicons, using primers surrounding the known sites of mutation. To broadly assess mutations, next generation sequencing (e.g., on an Illumina HiSeq 2000 platform) will be employed, using a paired end sequencing strategy of libraries constructed from tumor DNA. DNA will either be sequenced in its entirety from a whole genome library or will be first enriched for exonic sequences using the Agilent Sure Select system, aiming for 30X or 100X average coverage per base, respectively. The sequence fragments will be mapped back to the genome using the BWA algorithm. Of sequences overlapping a particular base pair in the genome, the percent mutant calls greater than 20% with a minimum of 25X coverage will be

considered as an arbitrary threshold for single nucleotide variants (SNVs). SNVs that are not present in the matched normal sample will be considered candidate somatic mutations.

A related technology, RNA-Seq, utilizes RNA from the tumor specimen to create a cDNA library for high-throughput sequencing. RNA-seq will be performed using Illumina kits followed by high-throughput sequencing on an Illumina HighSeq 2000 machine. The cutoffs for coverage and percent mutant calls mentioned above will also be used to identify putative SNVs. RNA sequencing will also be used to read out digital gene expression across the genome as described.

Recent advances in genomic technologies enable GEP at the single cell level, a distinct advantage over conventional GEP which cannot always distinguish tumor vs non-tumor gene expression([95](#), [96](#)). Single-cell approaches allow identification of the evolution of rare populations of resistant tumor cells, as well as identification of TME cells critical for the survival of the tumor. The Center for Cancer Research (CCR) has recently opened a single cell analysis core facility with expert staff headed by [name] within the CCR Genomics Core. This facility has the ability to take purified viably frozen cells banked from patient biopsies and prepare them, using well-validated 10X Genomics technology, for single-cell RNA sequencing. This core is directly integrated with the NCI Sequencing core facility to provide high-quality, deep-sequencing of the single cell RNA-SEQ samples, as well as ‘first-pass’ data processing and analysis. Data will then be transferred to lymphoma researchers and bio-informaticians in the [name] lab for further analysis of gene expression patterns and cellular population dynamics.

